13.4 Participant and Data Confidentiality

Participant confidentiality is strictly held in trust by the participating investigators, their staff, and the study sponsor. This confidentiality is extended to cover the clinical information relating to participants. Therefore, the study protocol, documentation, data, and all other information generated will be held in strict confidence. No information concerning the study or the data will be released to any unauthorized third party without prior written approval of the Principal Investigator.

13. Data Handling and Record Keeping

13.1. Data Collection and Management Responsibilities

Data collection is the responsibility of the clinical trial staff at the site under the supervision of the site PI. The investigator is responsible for ensuring the accuracy, completeness, legibility, and timeliness of the data reported.

All source documents should be completed in a neat, legible manner to ensure accurate interpretation of data. Black ink is required to ensure clarity of reproduced copies. When making changes or corrections, cross out the original entry with a single line, and initial and date the change. DO NOT ERASE, OVERWRITE, OR USE CORRECTION FLUID OR TAPE ON THE ORIGINAL.

Copies of the CRF will be provided for use as source documents and maintained for recording data for each participant enrolled in the study. Data reported in the CRF derived from source documents should be consistent with the source documents or the discrepancies should be explained and captured in a progress note and maintained in the participant's study record.

Clinical data (including AEs, concomitant medications, and expected adverse reactions data) and clinical laboratory data will be entered into paper case report forms. Clinical data will be entered directly from the source documents.

13.2. Study Records Retention

Study documents must be retained for a minimum of 3 years after the study's closure. No records will be destroyed without the written consent of the sponsor, if applicable. It is the responsibility of the sponsor to inform the investigator when these documents no longer need to be retained.

13.3. Protocol Deviations

A protocol deviation is any noncompliance with the clinical trial protocol, GCP, or MOP requirements. The noncompliance may be either on the part of the participant, the investigator, or the study site staff. As a result of deviations, corrective actions are to be developed by the site and implemented promptly.

It is the responsibility of the site to use continuous vigilance to identify and report deviations within 10 working days of identification of the protocol deviation. All deviations must be addressed in study source documents. Study deviations must be sent to the IRB per Riverside's guidelines. The site PI/study staff is responsible for knowing and adhering to IRB requirements.

13.4. Publication and Sharing Policy

Riverside and the PI retain the right to publish information related to the study so long as such publication or other public disclosure does not and is not reasonably anticipated to result in Stryker's loss of rights in or to Confidential Information, or Research Inventions. Prior to submission for publication of abstracts, manuscripts, presentations or other communications describing the results of any aspect of the study the party seeking to publish shall send Stryker a copy of each manuscript to be submitted via email to [contact], and allow Stryker at least forty-five (45) days to review a copy of the material intended for publications in order to redact any Confidential Information, or Research Inventions therefrom. Upon receipt of notice from Stryker Institution or Investigator shall expunge from any proposed publication or other public disclosure, and shall not publish or disclose, any information that Stryker reasonably believes would result in loss of rights in any Stryker Confidential Information, or Research Inventions or would otherwise compromise Stryker's rights or interests.

14. Study Administration

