14.2.1.1. Delegation of Responsibility

^{*}Significant Financial Interests: Income exceeding \$5,000 including salary, consultant payments, honoraria, royalty payments, dividends, loan, or any other payments or consideration with value. Equity in the form of stock, stock options, real estate, loan to, or any other investment or ownership interest exceeding \$5,000 (current market value) or a 5% or greater ownership interest. A management position (director, officer, partner, or trustee) with the interested entity.

The PI is responsible for providing training and supervision of study team members who perform tasks that are delegated by the PI. The PI is accountable for regulatory violations resulting from failure to adequately supervise the conduct of the research study.

15. Conflict of Interest Policy

The independence of this study from any actual or perceived influence, such as by the pharmaceutical industry, is critical. Therefore any actual conflict of interest of persons who have a role in the design, conduct, analysis, publication, or any aspect of this trial will be disclosed and managed. Furthermore, persons who have a perceived conflict of interest will be required to have such conflicts managed in a way that is appropriate to their participation in the trial. The study leadership in conjunction with the RMC IRB has established policies and procedures for all study group members to disclose all conflicts of interest and will establish a mechanism for the management of all reported dualities of interest. All members of the Study Team will disclose whether he/she or his/her spouse or dependent children have any significant financial interests related to the work to be conducted as part of the project, including the pharmaceutical or medical equipment company and other entities whose financial interests would reasonably appear to be affected by the outcome of the study.

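### Section 13.4 limits the company's publication control to confidential information and inventions, then adds an open-ended ground for removal that can be read to reach trial results

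*Protocol*

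**What the plan says.** Section 13.4 (Publication and Sharing Policy; the number 13.4 is used twice in the protocol) sets its rule in three sentences.

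- **Right to publish.** "Riverside and the PI retain the right to publish information related to the study", on condition that this does not cost the company, and is not reasonably expected to cost it, rights in Confidential Information or Research Inventions.
- **Review.** Abstracts, manuscripts, presentations and other "communications describing the results of any aspect of the study" go to the company before submission. The site must "allow Stryker at least forty-five (45) days to review", and the purpose is stated: "in order to redact any Confidential Information, or Research Inventions therefrom".
- **Removal.** Once notified, the site "shall expunge from any proposed publication or other public disclosure, and shall not publish or disclose, any information that Stryker reasonably believes" meets either of two tests. One is loss of the rights just named. The other is that it "would otherwise compromise Stryker's rights or interests".

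Section 15 (Conflict of Interest Policy) opens: "The independence of this study from any actual or perceived influence, such as by the pharmaceutical industry, is critical". It then requires that "any actual conflict of interest of persons who have a role in the design, conduct, analysis, publication, or any aspect of this trial" be disclosed and managed.

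Section 4.1 states that both devices compared, the Tritanium PL Cage and the AVS UniLIF PEEK Spacer, are the same company's products.

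**The concern.** The third sentence gives a ground for removal that the first two do not. They confine the company to two named categories. The third adds its rights or interests at large, and the company itself makes the judgement. A site following section 13.4 therefore cannot tell whether a request to remove a finding that is neither confidential information nor an invention is within the policy.

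What is at stake is selective reporting. The hypotheses in sections 2.2 and 9.2 look for an advantage of Tritanium, and section 3.1 hopes to show that it is an effective option. If endpoint or safety results can be removed from a manuscript because they harm the company's interests, readers see a filtered answer. No analysis method can repair that afterwards.

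**Working it through.** This is a point of wording, and the protocol gives no figure to reproduce. The check sets the sentences side by side.

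| Part of section 13.4 | What limits the company's control |
|---|---|
| Sentence 1, right to publish | Loss of rights in Confidential Information or Research Inventions |
| Sentence 2, purpose of review | Redaction of Confidential Information or Research Inventions |
| Sentence 3, duty to remove | Loss of those rights, **or** anything else compromising rights or interests |

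1. **Is the last ground separate?** Yes. It is joined by a disjunction and uses the word for *in some other way*, so it adds to the two categories and does not restate them. Sentence 3 is wider than the purpose in sentence 2 and the condition in sentence 1.
2. **Can it reach results?** The material under review is expressly reports of study results. The term for interests has no definition or limit in the section, endpoint and safety data are not exempted, and no arbiter is named. A company could reasonably believe that slow fusion, revisions or adverse events with its product harm its commercial interests. Coverage of results is thus an available reading of the plain words. It is an inference, because the clause does not mention unfavourable results.
3. **How does it sit with section 15?** That section states a principle of independence and a rule that persons' conflicts be disclosed and managed, with publication among the roles named. It contains no rule on a manufacturer's review or removal of text. The two sections are in tension at the level of principle.

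**Illustration of what sign-selection can do.** Inputs: 20 participants (section 5.3); equal allocation, so 10 per arm (assumed; section 9.4.1 gives permuted blocks but no ratio); a common true fusion rate p in both arms (assumed); a difference at one time point, shown only when it favours Tritanium (assumed).

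With X and Y independent Binomial(10, p) counts for Tritanium and PEEK, D = (X − Y)/10 and f the binomial probability:

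E[D | D > 0] = Σ_{x>y} ((x − y)/10) f(x) f(y) ÷ Σ_{x>y} f(x) f(y)

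| p | Numerator | P(D > 0) | Mean shown difference |
|---|---|---|---|
| 0.5 | 0.0881 | 0.412 | 0.214 |
| 0.7 | 0.0803 | 0.403 | 0.199 |
| 0.8 | 0.0694 | 0.388 | 0.179 |
| 0.9 | 0.0501 | 0.344 | 0.146 |

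The true difference is zero in every row. These values follow from the sample size and from complete suppression, and would be the same for any two-arm trial of this size. They do not measure this clause.

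**The case against.** **Unfavourable results are not mentioned, and the belief must be reasonable.** Both are true. The open-ended ground follows a reference to loss of proprietary rights and could be read as covering similar interests only. A reader might infer that the clause plainly covers, or was written to cover, bad results. The text does not support that; it supports only that the clause can be read that way. The reasonableness test is a real limit, but it does not take results out of reach.

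**Section 15 is not breached.** A reader might call this a contradiction between 13.4 and 15. It is not one, because section 15 sets no bar on company removal of text. The inconsistency that stands is inside section 13.4.

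**Key terms are not defined here.** Confidential Information and Research Inventions are capitalised without a definition in the text available, and a site agreement may define them. Any repair should therefore leave those definitions alone. Deleting the open-ended ground does not depend on them.

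**Oversight sees the data anyway.** The IRB assesses safety and efficacy by arm at least semiannually (section 7.7) and receives SAEs and a final report (section 14.2). The clause governs publication and other public disclosure only. This protects participants and keeps results from being hidden from oversight, but it does not put them in the public record.

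**Both arms belong to the company.** A between-arm difference is therefore not always against its interests. That weakens the motive for some results, though poor fusion or adverse events in either arm could still harm it.

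**The illustration is generic.** This stands in full. It takes fusion rates from outside the document, a single time point although section 9.3.1 compares four visits and the primary endpoint in section 4.2.1 is time to fusion, and total suppression in roughly 60% of trials (1 − 0.40 at p = 0.7).

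**Conclusion.** Section 13.4 is internally inconsistent. Its last sentence grants a removal right wider than the purpose and condition stated before it, on an undefined ground with no exemption for results. On its plain wording it can reach unfavourable endpoint or adverse event results for either cage, which leaves the published answer open to selective reporting. It is in tension with the principle that opens section 15, without breaching any rule there.

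The conclusion rests on the text of section 13.4 alone and needs no numerical assumption. How often the clause would be used, if ever, cannot be known from the document, so there is no estimate of bias; the range of about 0.15 to 0.21 shows only the worst that complete sign-selection could do with 10 per arm at true fusion rates of 0.9 to 0.5. The point concerns reporting. It touches no endpoint, sample size, allocation or analysis method. It should be corrected because the repair is small and the harm, if it occurred, could not be undone by analysis.

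**What to change.** - Delete from the last sentence of section 13.4 the words "would otherwise compromise Stryker's rights or interests" and the conjunction that joins them, so that the duty to remove matches the stated purpose of the review.
- Add one sentence, for example: *Results for the endpoints in section 4.2 and adverse event data may not be removed under this clause.* Worded this way, it limits the clause without redefining Confidential Information.
- Keep the review period of at least 45 days and the protection of confidential information and inventions.

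The cost is a wording amendment to the protocol, submitted to the IRB as section 12.2 requires, and the same change in the site agreement if it carries matching language. The company gives up a broad removal right; its protection of confidential information and inventions is otherwise unchanged. No study procedure, visit or analysis changes.

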14.1. Study Leadership

The Study Team will govern the conduct of the study. The Study Team will be composed of the Principal Investigator, the Operations Director, the Investigators, and the Research Coordinator. The Study Team will work closely together to carry out study activities and ensure compliance with the study protocol.

14.2. Investigator Responsibilities

The PI is responsible for ensuring that the research study is conducted in accordance with the clinical investigation plan, conditions of approval set by the RMC IRB, state and federal regulations, and ethical guidelines, affording the most protection to the subjects enrolled in this research study.

The investigators agree to the following:

- The project will be performed by qualified personnel according to the RMC IRB-approved protocol.
- Make no changes or deviate from the research protocol, except to protect the life and physical well-being of a subject in an emergency; in the event of such a deviation, it will be documented and explained.
- The equipment, facilities, and procedures to be used in this research meet recognized standards for safety.
- No change will be made to the human subjects protocol or consent form(s) until approved by the RMC IRB.

- Create and maintain source documents throughout the research study; ensure that all study-related materials are retained per institutional and protocol requirements.
- No subjects will be enrolled or data collected until the study is approved by the RMC IRB, and unless approval is current.
- Legally effective informed consent or assent will be obtained from all human subjects as required.
- Record, report, and assess every adverse event in accordance to the protocol; and report to the RMC IRB and sponsor all SAEs and device deficiencies that could have led to an SAE.
- Unanticipated problems, adverse events, and/or new information that occur in the course of the investigation that may affect the risk-benefit assessment for this research will be reported to the RMC IRB Office.
- Inform subjects of any new significant findings that occur during the study and provide him/her with procedures for possible emergencies related to the study, and make the necessary arrangements for emergency treatment.
- All named individuals on this project have read and understand the procedures outlined in the protocol and will be acting under my supervision.
- All named individuals on this project have completed the applicable CITI training program with a score of at least 80% or greater on every module, and have been given an opportunity to review the Belmont Report and The "Common Rule" (45 CFR Part 46).
- Student and guest investigators on this project are knowledgeable about the regulations and policies governing this research.
- I have read and understand the information in the Indications For Use document and Surgical Technique Manual, including potential side effects and risks of the device.
- I agree to maintain adequate and accurate records in accordance with the regulations and to make those records available for inspection in accordance with the regulations.
- I agree to cooperate with the IRB in the event it audits any or all of my IRB approved protocols to inquire about study progress or to observe the consent process that is used.
- I agree to meet with the investigator(s), if different from myself, on a regular basis to monitor study progress.
- If I will be unavailable, as when on sabbatical or other leave, including vacation, I will arrange for an alternate medical staff sponsor to assume responsibility during my absence. I will advise the RMC IRB by letter of such arrangements.
- I agree to promptly and completely comply with an IRB decision to suspend or withdraw its approval for the project.
- I agree to submit a final report to the IRB upon conclusion of the project.
- If I, or my spouse, or dependent children have any significant financial interests* related to the work to be conducted as part of the project, including the pharmaceutical or medical equipment company and other entities whose financial interests would reasonably appear to be affected by the outcome of the study, I have disclosed them below.

14.2.1.1. Delegation of Responsibility

^{*}Significant Financial Interests: Income exceeding \$5,000 including salary, consultant payments, honoraria, royalty payments, dividends, loan, or any other payments or consideration with value. Equity in the form of stock, stock options, real estate, loan to, or any other investment or ownership interest exceeding \$5,000 (current market value) or a 5% or greater ownership interest. A management position (director, officer, partner, or trustee) with the interested entity.

The PI is responsible for providing training and supervision of study team members who perform tasks that are delegated by the PI. The PI is accountable for regulatory violations resulting from failure to adequately supervise the conduct of the research study.

15. Conflict of Interest Policy

The independence of this study from any actual or perceived influence, such as by the pharmaceutical industry, is critical. Therefore any actual conflict of interest of persons who have a role in the design, conduct, analysis, publication, or any aspect of this trial will be disclosed and managed. Furthermore, persons who have a perceived conflict of interest will be required to have such conflicts managed in a way that is appropriate to their participation in the trial. The study leadership in conjunction with the RMC IRB has established policies and procedures for all study group members to disclose all conflicts of interest and will establish a mechanism for the management of all reported dualities of interest. All members of the Study Team will disclose whether he/she or his/her spouse or dependent children have any significant financial interests related to the work to be conducted as part of the project, including the pharmaceutical or medical equipment company and other entities whose financial interests would reasonably appear to be affected by the outcome of the study.

Appendix A: Radiographic Guidelines

GE Optima CT660

Type Multislice

of slices 64

GREEN FEATURES ≥60% lower CO2 emissions using energy-saving mode

DETECTOR

Field of view 50

Total detector width, z-axis, mm 40

Optional minimum rotation time, sec 0.35

Standard Rotation times, sec, 360° 0.4, 0.5, 0.6, 0.7, 0.8, 0.9, 1, 2

CLINICAL APPLICATIONS AND FUNCTIONALITY

Z-axis coverage for brain perfusion 32 cm

GANTRY

Gantry opening, cm 70

Gantry angle deg GENERATOR

Ma range 10-600, 5 increments

kW output 0.8-72

Kvp range 80, 100, 120, 140

TABLE FEATURES

Optional max load capacity, with restrictions, kg 227
Max load capacity without restrictions, kg 227

SYSTEM INTEGRATION

DICOM Yes Storage commitment SCU Yes ECG waveform SCP/SCU Yes Query/Retrieve SCU and SCP Yes Modality worklist SCU Yes CT image storage SCU/SCP Yes Modality performed procedure step SCU Yes Enhanced CT storage SCU/SCP Yes

IMAGE RECONSTRUCTION

Archive MiniSAS HDD, HDD

Computer cpu Intel E5540 DUAL 2.53 GHz Quad Core Xeon Processors QPI

Reconstruction matrices 512 x 512

FDA CLEARANCE Yes

CE MARK Yes

MARKETING REGION Worldwide

Criteria for evaluating spinal bony fusion

- No lucent area around the implant
- No presence of herniated disk, central stenosis, lateral recess stenosis, foraminal stenosis, facet anthropathy.
- No fracture of the device, graft, or vertebra
- Visible bone formation in or about the graft material
- Less than 3 degrees of inter-segmental position change on flexion and extension views
- Presence of subsidence: a migration of more than 3mm into the adjacent vertebra
- Proportion of bridging bone visually estimated over the surface area of the joint (i.e., 5%, 15%-30%, etc.).
